10.3 Concomitant Therapy

Therapy (medication and non-medication therapies) not restricted by a protocol requirement may be used during the study for the treatment or prevention of disease or to maintain good health. However, the subjects should not take concomitant medications that affect the BPH symptoms except for the stable dose at baseline out to the 3 month follow-up visit.

10.4 Summary of Study Procedure

The treatment for the study may be performed in an office, outpatient, ambulatory surgical, or hospital setting.

10.4.1 Peri-Procedural Medication

A 5-day course of oral antibiotic is recommended to be started up to 2 days prior to the procedure and completed after the procedure. An oral NSAID also may be given prior to the procedure.

Immediately pre-procedure, a urine analysis must be completed to verify no new active urinary infections have arose between screening and treatment.

There are three main pain medication protocol options used with the Rezūm procedure. Conscious sedation, a prostate block or oral medication. The first option is conscious sedation (propofol) and it may be done in clinic, an ambulatory setting, outpatient or hospital setting (per physician's recommendation). The second option is to use a local anesthesia in the form of a prostate block given 5-10 minutes before the procedure. The third option is oral medication, which includes an anti-anxiety medication (e.g., Valium or Xanax) and an oral analgesic (e.g. hydrocodone or oxycodone) given at least 45 minutes prior to the procedure. The physician has the discretion to prescribe anti-pain or other medications typically used during the rigid cystoscopy procedures. If administered, the use of these medications will be recorded in the case report form.

It is recommended that a bolus of lidocaine gel is injected into the urethra 10 minutes prior to beginning the Rezūm procedure. In general, the Rezūm procedure approach is similar to a rigid cystoscopy. Therefore, the same type of medication/anesthetic used with rigid cystoscopy procedures is recommended for the Rezūm procedure. If administered, the use of an anesthetic or sedative will be recorded in the case report form.

10.4.2 Rezūm Treatment

The objective of the treatment is to create contiguous, overlapping lesions running parallel to the natural slope of the urethra. Both pre-procedure cystoscopy and TRUS help to “map” or plan the ideal treatment. The total number of treatments in each lobe of the prostate is determined by the length of the hypertrophied prostatic tissue and can be customized to the configuration of the gland including the median lobe.

The Rezūm System should be prepared per the Instructions for Use. A compatible 4 mm, 30°, 30cm cystoscopy lens is inserted into the Rezūm Delivery Device and the cystoscopy camera and light source is attached to the Delivery Device, allowing the visual images to be viewed on a monitor. The distal tip of the Delivery Device is coated with a lidocaine gel or equivalent water soluble gel to lubricate the device prior to insertion into the urethra.

The Rezūm procedure is performed with the patient in the dorsal lithotomy position and the treatment device is inserted into the urethra. Confirmation of the contours of the prostate and planned disbursement of thermal lesions as derived from the baseline cystoscopy is recommended. Examination of the bladder and specifically the ureteral orifices is important, particularly in the event that median lobe tissue has elevated the orifice. Treatment begins with the needle tip visually positioned and inserted beginning approximately 1 cm distal to the bladder neck. It is suggested to complete all treatments on one side of the gland in order take advantage of the latent heat from prior treatments on that side, and then proceed to treat tissue on the contralateral side of the gland.

Multiple thermal treatments are delivered with the retractable vapor needle that penetrates a fixed 10.25 mm into the prostatic tissue. Each treatment delivers approximately 208 calories of thermal energy by converting 0.42 mL of sterile water into vapor thermal energy with the application of RF current to the inductive coil within the device. The treatment needle has a total of 12 small emitter holes spaced around its tip at 120° intervals to allow circumferential dispersion of thermal energy to create an approximate 1.5 to 2.0-cm lesion that remains confined within the anatomical zones of the prostate. A continuous saline (room temperature) flush irrigation through the device lumen enhances visualization and cools the urethral surface to preserve the urethral lining.

The prostate adenoma in the transition and central zones can be targeted. Any intravesical prostatic protrusions of either lateral or median lobes may be injected starting 1 cm from the proximal edge of the protrusion. Prior to treating the median lobe treatments angle the treatment needle at 45 degrees medially into the tissue. The treatment needle should be retracted after each treatment and repositioned in approximately 1-cm increments distal from the previous site to the end of the prostatic tissue just proximal to the verumontanum.

Upon removal of the Rezūm delivery device, a flexible cystoscope will be inserted into the subject's urethra to conduct an immediate post procedure (recorded) inspection of the bladder, trigone and ureteral orifices. Any incidences of bladder, trigone or ureteral orifice injury which should be visible as blanching, erythema, or other trauma immediately post-procedure should be reported and documented as an adverse event.

10.5 Follow-up

10.5.1 Prior to Discharge

There is potential for transient acute urinary retention occurring after any transurethral BPH procedure – the reported incidence ranges from 6.8% after a TURP, to a high of 23% after a treatment with the Prostiva RF device. Given subjects with prostates ≥ 80 cm³ are likely to receive a larger number of treatments (than with smaller prostates), including treatments of intravesical protrusions right at the bladder neck, it is required that each subject have an indwelling Foley catheter for a minimum of 7 days post the Rezūm procedure before attempting a voiding trial. A 16-French catheter is recommended. The incidence of urinary retention in the Rezūm II pivotal trial for prostates ≥ 30 to 80 gms was 4.4%.

The subjects should continue to stay on his BPH medication after the procedure under the physician's direction up to 3 months post procedure.

Antibiotics prior to catheter removal (7-10 days post procedure) is required. Physicians are required to onboard antibiotics 2 days prior to catheter removal and continue antibiotics for 3 days post catheter removal. The types of antibiotics to be prescribed will be left to physician discretion and potential resistance.

10.5.2 Post Treatment Care

During the post-treatment period, investigators will follow the current AUA guidelines in managing their subjects for the detection of prostate cancer in addition to the evaluations required by this protocol.

10.5.3 Scheduled Follow-up Evaluations

The following evaluations will be completed at each visit as indicated in Table 10-2. For the subset of subjects who agree to endoscopic evaluations, an examination will be performed at their 6 month visit after all the questionnaires have been answered.

TABLE 10-2: SCHEDULE OF VISITS

	Baseline Pre-Op	Intra Procedure	Discharge	Cath Removal	2 weeks	6 weeks	3 months	6 months	12 months	Annually to 3 years	Unscheduled	
Compliance window				Min. 7 days post	± 2 days	± 7 days	± 7days	± 30 days	± 30 days	± 60 days		
Physical Exam	√			Voiding Trial and, if appropriate, Indwelling Catheter removal*	√	√	√	√	√	√		
Medical History	√											
Blood Analysis (CBC, BUN, Blood Sugar, Serum Creatinine)	√				√							
Urine Analysis (Sugar, Protein, WBC/RBC, Bacteria)	√	√			√	√						
Abdominal and Pelvic Exam					√	√						
Uroflow (Qmax + PVR)	√					√	√	√	√	√	√	
Urodynamics Assessment	√								√ (optional)			
IPSS (Standard)	√					√	√	√	√	√	√	
IPSS (Acute)					√							
Additional Questionnaires: • IIEF • MSHQ-EjD • BPHII • EQ-5D-5L	√						√	√	√	√	√	
PGI-I QoL							√	√	√	√	√	
Resumption to Activities questionnaire					√	√ ¹						
Subject satisfaction questionnaire									√	√	√	
Prostate specific antigen (PSA)	√							√	√	√	√	
Intravesical Protrusion (TAUS)	√							√	√	√		

	Baseline Pre-Op	Intra Procedure	Discharge	Cath Removal	2 weeks	6 weeks	3 months	6 months	12 months	Annually to 3 years	Unscheduled	
Prostate volume (TRUS)	√							√	√	√		
Retroperitoneal ultrasound (renal and bladder)	√				√ ³	√						
Digital Rectal Exam (DRE)	√						√	√	√	√		
Rezūm Procedure		√										
Subject pain scale	√		√			√	√	√	√			
Adverse event(s) review		√				√	√	√	√	√	√	√
Medication(s) used	√	√	√			√	√	√	√	√	√	√
Flexible Cystoscopy (recorded)	√ ²	√ ²							√ ²			
CT Scan (Intravenous rectal and oral contrast)						√ ⁴ If needed	√ ⁴ If needed					

¹If subjects have not resumed to activities by 2 weeks, a repeat of the Resume to Activities Questionnaire should be done at the 6 week follow-up

²Videos to be reviewed by CEC to assess integrity to the bladder, trigone, or ureteral orifices

³Only required if subject's BUN and/or Creatinine level is abnormal from their baseline assessment

⁴Only required if subject answers "yes" to abnormalities in the abdominal and pelvic exam questions AND they have a positive infection identified from the urine culture then a CT Scan, or other exams deemed necessary are to be ordered.

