8.2.7 Rezūm II Study: Procedural pain management and catheterization

Investigators used varying combinations of pain and anxiety management during procedures based on their clinical judgment and standard of practice. Of the 196 subjects, 135 (68.9%) received oral sedation only, 41 (20.9%) had a prostate block, and 20 (10.2%) received conscious IV sedation.

Catheterization immediately post-procedure was performed at the discretion of the treating physician, frequently done to avoid effects of inflammation and swelling that might occur. A total of 90.4% (122/135) of treatment subjects were catheterized for a mean 3.4 ± 3.2 days. Of these catheterizations, 68% (83/122) were discretionary and 32% (39/122) were due to an unsuccessful voiding trial immediately following the procedure. In the control group, 19.7% (12/61) of subjects were catheterized for a mean 0.9 ± 0.8 days.

Subjects reported that time to resume usual activities after discharge, typically after removal of the catheter, was a median of 4 (0-90) days for the treatment group and 1 (0-15) day for the control group.

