11.1.9 Resumption to Activities

An assessment of when a subject resumed his normal activities after the Rezūm procedure will be evaluated.

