12.5.4 Ancillary Endpoint A4: Change in Quality of Life

Quality of Life (QoL) changes will be measured using the QoL question in the IPSS and BPH Impact Index (BPHII) and EQ-5D (a standardized instrument for use as a measure of health outcome) assessment and also the average time before subjects was able to resume pre-treatment activity.

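### Time to resume activity is not scheduled for collection after 6 weeks, so A4's average will be too short if any man is still unresolved then and is dropped or given his visit day

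*Combined protocol and SAP*

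**What the plan says.** Section 11.1.9 describes the instrument as "An assessment of when a subject resumed his normal activities after the Rezūm procedure". In Table 10-2 (section 10.5.3) its row is marked at 2 weeks and at 6 weeks only. Footnote 1 makes the 6-week entry conditional: for men who have not resumed by 2 weeks, "a repeat of the Resume to Activities Questionnaire should be done at the 6 week follow-up". The 6-week window is plus or minus 7 days. The cells for 3, 6 and 12 months, annual visits and unscheduled visits are empty.

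Section 12.5.4 lists among the A4 quality-of-life measures "the average time before subjects was able to resume pre-treatment activity". It does not define the average, and it says nothing about men who have not resumed when last asked. Section 10.8.1 states that the IPSS and other questionnaires are collected prospectively only. Section 10.5.4 allows some evaluations to be repeated at unscheduled visits, at the investigator's discretion. Section 10.6 refers missing-data handling to a separate SAP (CLP 3034-002), which is not part of the supplied text.

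For Rezūm II, section 8.2.7 reports that the time to resume usual activities "was a median of 4 (0-90) days for the treatment group", and that this was "typically after removal of the catheter".

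**The concern.** The schedule stops asking at a fixed point, and the men it stops asking about are those with the longest times. Any missing resumption dates are therefore not a random subset. If the average is taken over men with a recorded date, it describes only those who resumed within about 5 to 7 weeks. If unresolved men are entered at their 6-week visit day, their times are shortened. Both errors run in the same direction, towards faster recovery.

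Return to activity is a result that patients and clinicians read directly, and it may be set informally beside the Rezūm II figure. Dates that were never collected cannot be restored by an analysis rule written later.

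**Working it through.** The plan gives no expected mean, no expected share unresolved and no power statement for this measure, so there is no plan figure to reproduce. The check has two parts.

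**1. Can a resumption time fall outside the collection period?**

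- Last scheduled observation: 6 weeks = day 42, plus or minus 7 days, so day 35 to day 49 (Table 10-2).
- Longest time in the Rezūm II treatment group: 90 days (section 8.2.7).
- 90 > 49, so at least one Rezūm II man resumed after the latest day on which this trial is scheduled to ask.

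**2. How far could the average move?**

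This part is an illustration on assumptions. Let time to resumption be lognormal with median m and log-scale standard deviation s. Choose s so that the largest of about 135 men falls near 90 days:

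s = ln(90/m) / z, where z = Φ⁻¹(1 − 1/136) = 2.44

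With last questionnaire on day c:

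- true mean = m · exp(s²/2)
- share resolved: F = Φ[(ln c − ln m)/s]
- mean if unresolved men are dropped = true mean · Φ[(ln c − ln m − s²)/s] / F
- mean if unresolved men are given day c = F · (mean if dropped) + (1 − F) · c

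The documents give m = 4 for Rezūm II. The values 7, 10 and 14 are assumed, to allow for slower recovery here. Results for c = 42 and 88 men:

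| m (days) | s | Unresolved | Men of 88 | True mean | Dropped: mean (shortfall) | Visit day: mean (shortfall) |
|---|---|---|---|---|---|---|
| 4 | 1.28 | 3.3% | 2.9 | 9.0 | 6.7 (2.4) | 7.8 (1.2) |
| 7 | 1.05 | 4.4% | 3.8 | 12.1 | 9.5 (2.7) | 10.9 (1.2) |
| 10 | 0.90 | 5.5% | 4.9 | 15.0 | 12.0 (3.0) | 13.7 (1.3) |
| 14 | 0.76 | 7.5% | 6.6 | 18.7 | 15.2 (3.5) | 17.2 (1.5) |

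Shortfalls are taken before rounding. Over c = 35 to 49, the shortfall from dropping runs from 2.1 days (m = 4, c = 49) to 4.6 days (m = 14, c = 35).

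**Sensitivity to the tail (c = 42, unresolved men dropped)**

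- Light tail, m = 4 and s = 0.8: 0.16% unresolved, true mean 5.51 against 5.43, a shortfall of about 0.1 day. The expected longest time among 135 men is then 4 · exp(0.8 × 2.44) = 28 days, well under the 90 seen in Rezūm II.
- Heavy tail, m = 14 and s = 1.0: 13.6% unresolved, true mean 23.1 against 14.4, a shortfall of 8.7 days. The expected longest time is then 14 · exp(2.44) = 161 days, well beyond the Rezūm II range.

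**Effect on a median**

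In the four tabulated scenarios, dropping unresolved men at day 42 moves the median from 4 to 3.8, 7 to 6.6, 10 to 9.4 and 14 to 13.0 days. If they are kept as longer than their visit day, the median does not move.

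**The case against.** **The bias is conditional.** It needs at least one man unresolved at 6 weeks, and an analysis that drops him or uses his visit day. The documents establish neither. This stands, and the point is worded accordingly. The separate SAP may contain a censoring rule, but it could not supply dates that were not collected.

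**The form could still be repeated.** Section 10.5.4 permits discretionary repeats at unscheduled visits. A reader might infer from Table 10-2 that a slow man can never be asked again, but the documents support only that he is not scheduled to be. Discretionary repeats at visits prompted by an adverse event are not systematic collection.

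**The size could be made to look large.** A reader might place every late resumer at 90 days and assume 2%, 5% or 10% of them, with the rest averaging 10 days. The true mean is then 11.6, 14.0 or 18.0 days (for example 0.10 × 90 + 0.90 × 10 = 18.0) against a reported 10.0, which is 14%, 29% or 44% too low. Neither the shares nor the 10-day mean is in the documents, and 90 days is the single most extreme Rezūm II value. These percentages should not be cited as an estimate.

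**The longer catheter period does not prove a longer tail.** Section 10.5.1 requires at least 7 days, against a mean of 3.4 days among catheterised Rezūm II treatment subjects. That suggests a shift of several days, well inside 6 weeks. It makes slower recovery plausible but does not show that more men pass day 49.

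**The Rezūm II comparison is largely safe.** Rezūm II was reported as a median, which this gap barely touches, and A7 (section 12.5.7) does not name resumption time among its comparisons. A reader might infer that comparison with Rezūm II is lost. Only a comparison of means or upper ranges is affected.

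**Slow recovery shows elsewhere.** EQ-5D-5L usual activities and the BPH Impact Index are collected at 3 and 6 months, and adverse events carry resolution dates. These reveal delayed recovery but give no resumption date.

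**Conclusion.** The concern holds in its conditional form. The plan as written schedules no resumption date for a man still unresolved at his 6-week visit, and the supplied text does not say how he enters the A4 average. If he is dropped or given his visit day, the average is too short. The direction is certain, and the Rezūm II maximum shows that the situation is realistic.

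The size is not certain. On the assumed lognormal distributions with unresolved men dropped, it runs from about 0.1 day with a light tail to about 2 to 4 days when the tail is tied to the 0-90 day range. Entering the visit day roughly halves the latter. These figures depend on the assumed shape and medians, and on reading the undefined average as an arithmetic mean.

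The point is minor. A4 is ancillary and descriptive, carries no hypothesis, and does not enter the definition of study success in section 13. No primary or secondary conclusion, error rate or power is affected.

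**What to change.** **Footnote 1 of Table 10-2.** Replace the single repeat with: *If the subject has not resumed activities, the questionnaire is repeated at each following scheduled visit (6 weeks, 3 months, 6 months) until a resumption date is recorded.* Mark the 3- and 6-month cells accordingly.

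**Section 12.5.4.** Replace the average time with the Kaplan-Meier median and quartiles of time from procedure to resumption. Censor men who have not resumed at their last questionnaire, and report the number not resumed at each visit.

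The analysis change alone would protect the central summary under the existing schedule, provided most men have resumed by 6 weeks. The added collection is what recovers the tail and the late dates.

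**Cost.** One short form for a few men at visits that already take place, and one line of analysis text. The reported recovery time may come out slightly longer.

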10.5.4 Unscheduled Follow-up Visits

If subjects are seen for unscheduled/interim visits because of an AE, appropriate Case Report Form(s), including the AE CRF, will be completed, if applicable. At the investigator's discretion, some of the evaluations and tests may be repeated, if indicated. Sponsor requests that if any additional tests or procedures listed within this protocol are performed during an unscheduled visit the investigator provide the results on the Unscheduled Visit CRF.

10.6 Alternate BPH Treatments

Subjects who opt for alternate BPH treatments within 6 months of their treatment will be considered to have failed the treatment for the primary efficacy analysis. Additionally, subjects whom discontinue their BPH medication 3 months post-procedure and then resume prior to the 6 month visit will be considered a treatment failure. Alternate treatments include BPH medications (only if given to treat BPH symptoms), PUL, Prostiva RF, TURP, TUMT, laser, etc. Refer to Statistical Analysis Plan (CLP 3034-002) for missing data handling instructions.

10.7 Multiple IPSS Responses

If a subject has multiple IPSS baseline responses, the last baseline value prior to the procedure will be used in the analysis.

If a subject has multiple post-baseline IPSS responses within the same time visit window period, the average results will be used for the subject in all analyses unless there is scientific valid reason(s) to exclude one or more of the responses.

10.8 Follow-up Procedures

10.8.1 Lost to Follow-up

If a subject fails to comply with follow-up evaluations, the investigational site must make at least three attempts to contact the subject. Each attempt to contact the subject and the method used (e.g., telephone contact, registered letter) must be documented in the subject's records.

If a subject misses one of the follow-up evaluations, but is present at the subsequent follow-up, the subject can be readmitted into the study and queried retrospectively for basic information (e.g., AEs); however, the missed evaluation must be documented on a Protocol Deviation CRF. The IPSS and other questionnaires will be collected prospectively only.

10.8.2 Subject Withdrawal from Study

10.8.2.1 Voluntary Withdrawal

A subject may voluntarily withdraw from the study at any time. If a subject officially withdraws from the study, the investigator must ensure that the reason for the withdrawal is documented. If the subject has any device and/or procedure related AEs, the investigator should continue contact

with the subject until the resolution of the AE(s), if possible. Data from these subjects will be included in the analysis up to the point of each subject's withdrawal.

10.8.2.2 Data Withdrawal Due to Exclusion Criteria

A subject's data may be excluded from the analysis if the subject is later found not to meet one or more major exclusion criteria. The major exclusion criteria that would cause the withdrawal of the subjects' data are:

- Failure to obtain an informed consent prior to treatment;
- Subject has a baseline IPSS score of <13;
- Subject had an evidence of an atonic neurogenic bladder evaluated by a urodynamic assessment;
- Subject had a urethra contracture or stricture;
- Subject had a psychiatric condition that prevents him from adequately answering the study questionnaires;
- Subject had a neuromuscular disorder that will confound the results; or
- Subject has a prostate volume outside of the $>80 \text{ cm}^3$ to $\leq 150 \text{ cm}^3$ range.

The decision to exclude the subject's data from analysis will be decided by the CEC.

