
Primary Endpoints:
	
Primary Efficacy Endpoint The proportion of the intent-to-treat (ITT) analysis population that responds to therapy must be statistically significantly greater than 50%. A responder is defined as a subject who has an IPSS improvement $\geq 30\%$ post-treatment compared to baseline.
 
Primary Safety Endpoint – Post Procedure Device Related Serious Complications: Demonstration that the composite rate of post procedure device related serious complications in treated subjects is statistically significantly less than 12% at 6 months. These composite device-related serious complications for this endpoint are defined as:
 
 • Perforation of the rectum or GI tract • Formation of fistula between the rectum and urethra • Permanent damage to the bladder, trigone or ureteral orifices requiring intervention • Grade 2 hydronephrosis

Secondary and Ancillary Endpoints:	Secondary Endpoint S1: Device-related retention catheterization rate
	Secondary Endpoint S2: Absolute IPSS improvement at 6 Months
	Secondary Endpoint S3: Percent Responder at 1 year
	Secondary Endpoint S4: Percent Responder at 2 years
	Secondary Endpoint S5 Percent Responder at 3 years
	Ancillary Endpoint A1: Additional Responder Analyses
	Ancillary Endpoint A2: Change in Qmax and PVR
	Ancillary Endpoint A3: Change in Sexual Function
	Ancillary Endpoint A4: Change in Quality of Life
	Ancillary Endpoint A5: Procedure Parameters
	Ancillary Endpoint A6: PGI-I Questionnaire
	Ancillary Endpoint A7: Rezūm II Comparisons
Principal Investigator:	[name] Professor of Surgery Sydney Adventist Hospital Clinical School University of Sydney [name]
Sponsor, Study and Data Management:	NxThera, a Boston Scientific Company [name] [name] [contact]
Study Monitors:	US Monitoring: IMARC Research Inc. [name] [name] AUS Monitoring: TBD

2 List of Abbreviations and Phrases

AE	Adverse Event
AUASI	American Urological Association Symptom Index
AUR	Acute Urinary Retention
AUR	Acute Urinary Retention
BCI	Bladder Contractility Index
BOOI	Bladder Outlet Obstruction Index
BPH	Benign Prostatic Hyperplasia; also known as Benign Prostatic Hypertrophy
BPHII	BPH Impact Index
BUN	Blood Urea Nitrogen
CEC	Clinical Events Committee
CRF	Case Report Form
CV	Curricula Vitae
DRE	Digital Rectal Exam
DU	Detrusor Underactivity
EC	Ethics Committee
ED	Erectile Dysfunction

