9.3.2 Primary Safety Endpoint – Post Procedure Device Related Serious Complications

For the primary safety endpoint to be met, the proportion of the treated analysis population that experiences a safety composite event must be statistically significantly less than 12%.

These composite device-related serious complications for this endpoint are defined as:

- Perforation of the rectum or GI tract
- Formation of fistula between the rectum and urethra
- Permanent damage to the bladder, trigone or ureteral orifices requiring intervention
- Grade 2 hydronephrosis

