10.8.2.3 Involuntary Withdrawal

A subject also may be withdrawn by the investigator if the subject's participation in the study will have a negative effect on the safety of the subject. Data obtained up to the date of the subject's withdrawal will be included in the study, if applicable.

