12.4 Secondary Endpoints

The secondary endpoints include an assessment of IPSS on a continuous scale and additional responder analyses at different follow up time points. All secondary endpoints will be analyzed based on the treated analysis population consisting of subjects treated with the Rezūm System.

For all secondary endpoints based on IPSS scores, treated subjects who chose alternate treatments other than the assigned treatment prior to the end of the endpoint's follow-up period will be considered failures and their baseline value will be used as their imputed follow-up IPSS score for the secondary endpoint analysis.

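### Section 10.8.2.2 lets the CEC drop a treated man's data from an unnamed analysis for late-found ineligibility, with no deadline, masking or pre-procedure evidence rule; applied to primary safety, this would conflict with the treated population.

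*Combined protocol and SAP*

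**What the plan says.** Section 10.8.2.2 provides that a subject's "data may be excluded from the analysis if the subject is later found not to meet one or more major exclusion criteria". It then introduces a closed list: "The major exclusion criteria that would cause the withdrawal of the" subjects' data. The seven items are missing consent, low baseline IPSS, atonic neurogenic bladder, urethral contracture or stricture, a psychiatric condition affecting the questionnaires, a confounding neuromuscular disorder, and prostate volume out of range. The decision to exclude a subject's "data from analysis will be decided by the CEC".

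The neighbouring rules keep data. For voluntary withdrawal (10.8.2.1), "Data from these subjects will be included in the analysis up to the point of each" subject's withdrawal. For involuntary withdrawal (10.8.2.3), data up to the date of "withdrawal will be included in the study, if applicable".

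The synopsis requires that the composite rate "in treated subjects is statistically significantly less than 12% at 6 months". Section 9.3.2 says that "the proportion of the treated analysis population that experiences a safety composite event must be statistically significantly less than 12" percent. The only description of that population is in Section 12.4: "All secondary endpoints will be analyzed based on the treated analysis population consisting of subjects treated with the" device. It carries no eligibility condition.

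Primary efficacy is on ITT in the synopsis and Section 12.1, but on a modified ITT set in Section 9.3.1, which is not defined. Section 9.1 equates ITT with enrolled subjects. Section 10.2 makes full eligibility part of enrolment, while Section 17.8.3 lists enrolling an ineligible subject as a protocol deviation.

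**The concern.** This is a single-arm trial tested against fixed goals of 50% and 12%, so the result depends directly on who is in each denominator, and no control arm offsets a selective removal. The stated error rates hold if removals are unrelated to outcome. The text reviewed does not secure that.

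The issue is sharpest for safety. The CEC adjudicates the primary safety events (12.2), makes the final call on new ultrasound abnormalities (11.7) and reviews the post-procedure cystoscopy recordings (11.4 and Table 10-2). It will know who had an event when it decides whose data stay.

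The list does not fully prevent this, because not every item is anchored before treatment. The urethral contracture or stricture item is undated, and urethral stricture is also an anticipated adverse event in Section 14.4. A finding that arose after treatment could therefore be read as an entry failure. Late discovery is plausible for another item too: urodynamic tracings go to an independent reviewer with no stated read time (11.2).

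**Working it through.** **Inputs.** N = 88 (12.1). Safety: exact binomial against 12%, one-sided 5% (12.2). Efficacy: exact binomial against 50%, one-sided 2.5%, assumed responder rate 67.5% (12.1, 12.3). The documents give no number of removals and no rate of late-found ineligibility; both are assumed below.

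**1. The plan's own figures.** The safety p-value is P(X ≤ x | n, 0.12). At n = 88, five events give 0.0393 (pass) and six give 0.0846 (fail), which matches the stated limit of five. The efficacy p-value is P(X ≥ r | n, 0.5). The smallest passing count at n = 88 is 54, with type I error 0.0211 and power 0.909 at 67.5%, which matches the planned 90%.

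**2. How few removals change a result.**
- Safety, one event subject removed: 6/88, p = 0.0846 (fail), becomes 5/87, p = 0.0423 (pass).
- Safety, two removed: 7/88, p = 0.1571, becomes 5/86, p = 0.0457 (pass).
- Efficacy, one non-responder removed: 53/88, p = 0.0347, becomes 53/87, p = 0.0265 (still fails).
- Efficacy, two removed: 53/86, p = 0.0199 (pass).

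**3. Upper bound.** The safety limit stays at five for n = 85 to 88. If m event subjects could always be removed, type I error is P(X ≤ 5 + m | 88, 0.12): 0.0846, 0.1571 and 0.2571 for m = 1, 2, 3, against 0.0393 with none. For efficacy the critical counts at n = 87 to 83 are 54, 53, 53, 52, 51. The bound P(X ≥ critical count | 88, 0.5) is 0.0211, 0.0347, 0.0347, 0.0546 and 0.0827 for one to five removals. These bounds assume that whenever the trial misses narrowly, enough of the unfavourable subjects also have a listed failure.

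**4. Requiring the listed failure to be present.** Let each man have a listed failure with probability q, independent of outcome, and let every removal that helps the result be made. For safety, sum P(X = x) × P(M ≥ number needed), with M binomial(x, q). For efficacy, M is binomial(88 − x, q).

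Safety at q = 5%, term by term:
- five or fewer events: 0.0393
- six events, one removal needed: 0.0453 × 0.2649 = 0.0120
- seven events, two needed: 0.0725 × 0.0444 = 0.0032
- eight events, three needed: 0.1000 × 0.0058 = 0.0006
- total: 0.0551

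| q (assumed) | Safety type I (nominal 5%) | Efficacy type I (nominal 2.5%) |
|---|---|---|
| 1% | 4.2% | 2.2% |
| 2% | 4.5% | 2.3% |
| 3% | 4.8% | 2.6% |
| 5% | 5.5% | 3.1% |
| 10% | 7.5% | 5.5% |

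**5. Removals unrelated to outcome.** Safety type I error is 3.9-4.9% (n = 88 to 85) and efficacy 1.5-2.4% (n = 88 to 83), all within nominal. Power at 67.5% is 87.0-90.1% with one to five removed, against 90.9% with none.

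**The case against.** Section 10.8.2.2 never mentions safety, and several listed grounds point to efficacy: baseline IPSS, ability to answer questionnaires, a confounding disorder. A reader might infer that the rule flatly contradicts the treated population. The text supports only a conditional conflict, if the rule is applied to safety. That stands, but nothing in the section exempts safety.

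A reader might also take 8.5%, 15.7% or 25.7% as the safety error rate. Those figures need an event and a listed entry failure in the same men each time the trial narrowly misses, and the documents support no such coincidence. Even with always-favourable use, safety stays within nominal up to an assumed 3% failure rate and efficacy up to 2%. This stands. Error would be higher if failures clustered among event men, but nothing in the documents shows that they do.

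The efficacy side is weaker. Sections 9.1 and 10.2 can be read as placing an ineligible man outside ITT from the start. It is tempting to infer that the CEC decides knowing IPSS results, but no section routes IPSS to it. One removal cannot rescue the test. The unavailable SAP (CLP 3034-002) may define modified ITT, a decision deadline or masking, although Section 10.6 cites it only for missing data.

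The closed list, its objective items (consent, baseline IPSS, prostate volume) and three independent physicians (19.1) are real safeguards. The permissive and mandatory wordings can be reconciled by reading the list as grounds and the CEC as deciding whether to apply them, so little weight rests on that contrast.

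**Conclusion.** The concern holds as an open rule that should be closed, chiefly for safety. As written, a committee that knows who had a primary safety event may remove a treated man from an unnamed analysis at any time, on evidence that need not pre-date treatment. One such removal is enough to reverse a narrow safety failure; efficacy needs at least two.

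The realistic size is modest and rests on assumption. With a listed-failure rate of 1-10%, independent of outcome and always used favourably, type I error is about 4.2-7.5% for safety and 2.2-5.5% for efficacy. The larger safety figures are upper bounds only. Outcome-neutral use does no material harm to type I error or power.

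The documents do not show that the rule was meant for safety, that it defines the modified ITT set, or that anyone intends selective removal. It should be fixed because the repair is cheap and both primary endpoints must be met for study success (Section 13). Confidence is medium, since the separate SAP could not be checked.

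**What to change.** Amend Section 10.8.2.2 as follows:
- The primary safety analysis keeps every treated subject, except where consent law requires removal.
- The primary 6-month responder result is also reported in all subjects in whom the device was inserted, whatever is later found about eligibility.
- Any exclusion on a listed criterion applies only to an efficacy sensitivity set. It rests on pre-procedure evidence, is fixed before 6-month outcomes are reviewed, and is decided without reference to the subject's outcome.
- Every exclusion is reported with its reason.

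Use one ITT definition across Sections 9.1, 9.3.1, 10.2 and 12.1, saying whether an ineligible man in whom the device was inserted is included, and align the separate SAP with it. No separate reviewer panel is needed.

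The cost is protocol and SAP wording. The downside is that a few ineligible men stay in the primary denominators, with the sensitivity result shown beside them.
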